14.2.1.2 Immunogenicity Analysis Set for FVIII $\leq 2\%$

The immunogenicity analysis set of PTPs (> 50 EDs) with baseline FVIII \leq 2% (IAS2) and with no history of inhibitor prior to study entry will be a subset of the safety analysis set.

14.2.2 Effectiveness Analysis Set for Bleeding Episodes

The effectiveness analysis set for bleeding episodes (EASBE) will consist of all data for all subjects who report at least 1 new bleeding episode treated with ADVATE reconstituted in 2 mL SWFI.

14.2.3 Effectiveness Analysis Set for Prophylactic Treatment

The effectiveness analysis set for prophylactic treatment (EASPT) will include all subjects who were assigned by their Medical Doctor (site investigator) as being on prophylactic treatment during the whole course of this study.

14.2.4 Pharmacokinetic Analysis Set

The PK analysis set (PKAS) will include all subjects with one or more determinations of IR.

14.2.5 Surgical and Dental Procedures Analysis Set

The effectiveness analysis set for surgical and dental procedures (EASSDP) will include all subjects who underwent surgical or dental procedures during the study.

14.3 Handling of Missing, Unused, and Spurious Data

There will be no imputation on any outcome measure in this study. Missing data will be reported as such.

If a subject weight is missing from any infusion record, the subject's last recorded weight will be used to calculate the weight-adjusted dose.

If FVIII activity levels are reported as inequalities, the < or > sign will be dropped for use in numeric analyses.

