Study 060103 was a Phase 3b study that investigated the safety and efficacy of ADVATE in 55 PUPs under 6 years of age with severe or moderately severe hemophilia A. vi Of 517 treated bleeding episodes, 90% were managed with 1 or 2 infusions. Hemostatic efficacy was considered excellent or good in 93% of 466 rated bleeding episode treatments. Twenty-seven surgical procedures were performed, with intra- and postoperative hemostatic efficacies considered excellent or good in 22/22 (100%) and 25/25 (100%) of the procedures rated, respectively. Inhibitory antibodies to FVIII developed in 16/55 (29.1%; 95% CI: 17.1%-41.1%) subjects. All the subjects who developed inhibitors had severe hemophilia (FVIII <1%). At the time of inhibitor diagnosis, 7 subjects were categorized with high-titer inhibitors (>5 BU/mL confirmed with a new blood sample) and 9 subjects were categorized with low-titer inhibitors (≤5 BU/mL). An immunogenicity analysis set of 50 subjects was used for the calculation of the odds ratio (OR) of risk factors for inhibitor development, which included all 16 subjects with inhibitors and subjects without inhibitors who had at least 10 EDs. Univariate analysis identified statistically significant OR results for 3 risk factors: family history of inhibitor (4.95 [95% CI: 1.29-19.06]), non-Caucasian ethnicity (4.18, [95% CI: 1.18-14.82]), and intensive treatment at high dose^{vii} within the first 20 EDs (4.50, 95% CI: 1.05-19.25). Intensive treatment at high dose in all but 1 subject, where it was administered for a bleeding episode, consisted of perioperative infusions in the context of port placement. Inhibitor incidence in low-risk subpopulations of subjects who lacked the risk factors confirmed in this study was also examined. While 16/55 (29.1%) subjects in the entire study population developed inhibitors, 7/37 (18.9%) subjects who were Caucasian and 2/25 (8.0%) subjects who were both Caucasian and had no family history developed inhibitors. In the 20 subjects who were Caucasian, had no family history of inhibitors, and did not receive intensive treatment at high dose (lacked all 3 risk factors) there was no inhibitor development (0/20 [0.0%]). No subjects died or withdrew due to AEs. A total of 931 AEs were reported: 46 SAEs and 885 non-serious AEs. All 16 SAEs considered related to the administration of ADVATE were inhibitor development. There were 14 non-serious AEs considered related to the administration of ADVATE; of these, 6 were rated as mild and 8 were rated as moderate.

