10.3.2 Interval and Termination Visits

The following data, if available, will be collected at **interval and termination visits**:

- Height (cm)
- Weight (kg)
- Treatment regimen (eg, prophylaxis or on-demand) with ADVATE reconstituted in 2 mL SWFI
 - Weight adjusted dose and dosing interval (frequency of infusions)
 - Regimen change date
- All serious and non-serious AEs, regardless of causal relationship to ADVATE reconstituted in 2 mL SWFI
- All local and general, hypersensitivity and infusion-related reactions (see Appendix A for example only)
- FVIII inhibitor titer
- Serology for HCV and HIV-1/2, if available
- FVIII IR (IU/dL per IU/kg)
- Total ED from ADVATE reconstituted in 2 mL SWFI during study
- Total ED from all FVIII therapies

- Concomitant medications, including vaccinations
- Bleeding episodes, including anatomical location, etiology, and severity
- Subjective hemostatic effectiveness rating of excellent, good, fair, or none for each bleeding episode
- Number of ADVATE reconstituted in 2 mL SWFI infusions used to treat each bleeding episode
- Total units of ADVATE reconstituted in 2 mL SWFI administered to treat each bleeding episode
- Overall effectiveness assessment for prophylaxis for subjects who are on a prophylactic regimen for full duration of study (6 months), at termination visit
- Number of days subject missed from school/daycare due to each bleeding episode
- Number of days subject's caregiver missed from work/school/normal daily activities due to each bleeding episode

Details on the procedures to be performed at each study visit, including screening, can be found in Supplement 21.1 Schedule of Study Procedures and Assessments.

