11.1.9 Assessment of Adverse Events

Each AE from the first study product exposure until study completion/discontinuation date will be described on the AE CRF (ie, 1 AE per form) using the medical diagnosis (preferred), or, if no diagnosis could be established at the time of reporting the AE, a symptom, or sign, in standard medical terminology in order to avoid the use of vague, ambiguous, or colloquial expressions (see definition in Section 11.1). Each AE will be evaluated by the investigator for:

- Seriousness as defined in Section 11.1.1
- Severity as defined in Section 11.1.3
- Causal relationship to study product exposure or study procedure as defined in Section 11.1.4
- Local and general, hypersensitivity and infusion-related reaction as defined in Section 11.1.5

For each AE, the outcome (ie, recovering/resolving, recovered/resolved, recovered/resolved with sequelae, not recovered/not resolved, fatal) and action taken (ie, dose increased, dose not changed, dose reduced, drug interrupted, drug withdrawn) will also be recorded on the AE CRF. Recovering/resolving AEs will be followed until the study completion/termination visit. If the severity rating for an ongoing AE changes before the event resolves, the original AE report will be revised (ie, the event will not be reported as separate AE). During the course of any AE, the highest severity rating will be reported.

Deviations from the protocol-specified dosage (including overdosing, underdosing, abuse, and withdrawal), treatment errors (including incorrect route of administration, use of an incorrect product, and deviations from the protocol-defined dosing schedule),

failures of expected pharmacological actions, and unexpected therapeutic or clinical benefits will be followed with regard to occurrence of AEs, lack of efficacy, and/or other observations because these events may be reportable to regulatory authorities.

If an investigator becomes aware of an SAE occurring in a subject after study completion, the SAE must be reported on the SAE Form within 24 hours after awareness; no additional reporting on CRFs is necessary.

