14.4.1 Primary Outcome Measure

The primary outcome measure is to assess the incidence of all local and general, hypersensitivity and infusion-related reactions, irrespective of product-related causality for the AEs. The SAS will be employed to compute this outcome measure.

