14.4.2 Secondary Outcome Measures

Each secondary outcome measure will be calculated by employing the applicable analysis set:

- Number of AEs considered by the investigator to be causally related (possibly or probably related) to ADVATE reconstituted in 2 mL SWFI, SAS
- Number of inhibitors in all subjects, SAS

- Number of inhibitors in PTPs (>50 EDs) with baseline FVIII < 1% and with no history of inhibitors prior to study entry, IAS1
- Number of inhibitors in PTPs (> 50 EDs) with baseline FVIII ≤ 2% and with no history of inhibitors prior to study entry, IAS2
- Subjective hemostatic effectiveness rating of excellent, good, fair, or none for each unique bleeding episode treated, EASBE
- Number of bleeding episodes treated with 1, 2, 3, ≥ 4 infusions of ADVATE reconstituted in 2 mL SWFI, EASBE
- Total units of ADVATE reconstituted in 2 mL SWFI administered to treat each bleeding episode, EASBE
- Overall effectiveness of prophylaxis in subjects who are on a prophylactic regimen for the full duration of the study, EASPT
- Global assessment rating of hemostatic effectiveness of ADVATE reconstituted in 2 mL SWFI (excellent, good, fair, or none) in surgical or dental procedures, EASSDP
- Change in FVIII treatment satisfaction and preference ratings from caregiver between ADVATE reconstituted in 5 mL and 2 mL SWFI, SAS
- Change in FVIII infusion volume and time to mix and infuse FVIII treatment between ADVATE reconstituted in 5 mL and 2 mL SWFI, SAS

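### Section 14.3 bans imputation on every outcome, leaving no room for a conservative count of AEs with missing causality or a worst-case bound on unrated bleeds and procedures

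*Protocol*

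**What the plan says.** Protocol section 14.3 sets the missing-data rule: "There will be no imputation on any outcome measure in this study. Missing data will be reported as such". The section then gives two field-specific rules: a missing weight is replaced by the last recorded one, and inequality signs on FVIII levels are dropped. It has none for AE classification or effectiveness ratings.

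Three groups of outcomes depend on an assigned classification or rating:

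- **Primary (14.4.1):** "incidence of all local and general, hypersensitivity and infusion-related reactions, irrespective of product-related causality for the AEs. The SAS will be employed". It does not depend on causality, but it does depend on whether an AE is classed as a reaction.
- **Related AEs (14.4.2):** "Number of AEs considered by the investigator to be causally related (possibly or probably related) to ADVATE reconstituted in 2 mL SWFI, SAS".
- **Effectiveness (14.4.2):** a four-category rating for each treated bleed and each procedure. The analysis sets (14.2.2, 14.2.5) require a treated bleed or a procedure, not a rating. Section 14.4 promises frequencies and percentages and names no denominator.

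On completeness, section 11.1.9 says "Each AE will be evaluated by the investigator for" seriousness, severity, causality and reaction class. Section 10.3.2 opens its list of visit data with "The following data, if available, will be collected at", and section 10.5.2 makes diary completion voluntary.

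**The concern.** In a safety surveillance study, an AE whose causality cannot be resolved by query is usually counted as related, so that gaps in the record do not make the product look safer. Section 14.3 covers every outcome measure, so an analysis plan that adopted this convention, or a bound scoring unrated bleeds as None, would contradict the protocol. This cannot simply be left to the analysis plan.

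For related AEs the direction is certain. An event with no causality assigned is not among those considered possibly or probably related, so blanks can only reduce the count. The same applies to the primary incidence if the reaction class is blank. For ratings, the issue is that a reader cannot see how far missing ratings could move the result.

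**Working it through.** **Planning figure.** Enrolment reproduces: 60 / (1 − 0.17) = 72.3, rounded up to 73. This point does not affect it.

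**Bleed ratings, study 060103 (section 6.4.1; illustration only).** Inputs: "Of 517 treated bleeding episodes, 90% were managed with 1 or 2 infusions" and "Hemostatic efficacy was considered excellent or good in 93% of 466 rated bleeding episode treatments". Assumption: the two counts are in the same unit.

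- Reported figure: 0.93 × 466 = 433.4, so about 433; 433/466 = 92.9%, which agrees with 93%.
- Unrated: 517 − 466 = 51; 51/517 = 9.9%.
- Every unrated bleed a failure: 433/517 = 83.8%.
- Every unrated bleed excellent or good: (433 + 51)/517 = 484/517 = 93.6%.
- Break-even: the all-bleed percentage falls below 93% only if fewer than 93% of the unrated bleeds were excellent or good.

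**Procedure ratings (same section).** In 060103, 27 procedures were performed, and all 22 intraoperative and all 25 postoperative ratings were excellent or good. Over all 27, with unrated as failure: 22/27 = 81.5% and 25/27 = 92.6%. In 069902, with 65 procedures: 61/65 = 93.8% and 62/65 = 95.4%. Each was reported as 100% of the procedures rated.

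**Related AEs (scale from 060103; missing rates assumed).** The protocol gives no rate of missing causality. Related AEs were 16 serious + 14 non-serious = 30 of 931, or 3.2%. The table adds the stated share of 931 AEs, none of them among the 30, as related:

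| Assumed missing causality | Added AEs | Related AEs |
|---|---|---|
| 1% | 9 | 39/931 = 4.2% |
| 2% | 19 | 49/931 = 5.3% |
| 5% | 47 | 77/931 = 8.3% |

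The planned measure is the number and type of related AEs, so the percentages only show relative size.

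**Primary incidence (counts assumed; 60 subjects).** Assume each unclassified AE belongs to a different subject with no counted reaction. Each then adds 1/60 = 1.7 percentage points. Exact 95% intervals:

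| Subjects with a classified reaction | Incidence without unclassified AEs | Subjects added | Incidence with them |
|---|---|---|---|
| 0 | 0% (0 to 6.0) | 1 | 1.7% (0.0 to 8.9) |
| 0 | 0% (0 to 6.0) | 3 | 5.0% (1.0 to 13.9) |
| 2 | 3.3% (0.4 to 11.5) | 2 | 6.7% (1.8 to 16.2) |

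**The case against.** The strongest reply is that the rule's second sentence already handles the problem. Showing related, not related and missing AEs side by side discloses the gap, and nothing in the protocol turns a blank into an unrelated event. That is right: no AE is lost as an AE. But disclosure is not a conservative count, and the rule still forbids one.

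Blanks may also be rare. The investigator must rate each AE, the AE section (11.1) does not carry the qualifier found in 10.3.2, reactions have a supplementary questionnaire (11.1.5), and sponsor data clarifications are foreseen (18.2). This lowers the likely size but does not remove the direction. The voluntary diary bears more on home bleed ratings than on causality, which the investigator assigns.

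A reader might go further and infer three things that the documents do not support:

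- **That unrated bleeds are excluded from a success rate.** The protocol defines no success rate and fixes no denominator, and a not-rated row over all treated bleeds satisfies 14.3 as written. The way 060103 was reported is background, not a rule for this study. The denominator may properly be set in the analysis plan.
- **That missing ratings flatter effectiveness.** This needs unrated bleeds to have gone worse than rated ones. No passage says so, and the investigator rates bleeds treated in hospital or clinic (12.1.1). The 84% to 94% range lies on both sides of 93%, though mostly below it.
- **That missing causality distorts the primary outcome.** It cannot, because that outcome disregards causality.

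One tempting remedy also fails: counting every unclassified AE within 24 hours of an infusion as a reaction. Section 11.1.5 allows later reactions. At the 3 to 4 infusions a week that 8.6.3 quotes for prophylaxis under age 6, 3/7 = 43% to 4/7 = 57% of follow-up lies in that window, so unrelated childhood illness would be swept in.

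**Conclusion.** The point stands in a limited form. Taken literally, section 14.3 prohibits a conservative count of AEs with unresolved causality, so missing causality can only understate the related-AE outcome. It equally prohibits a worst-case bound on unrated bleeds or procedures. The primary outcome is exposed only through a blank reaction class.

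The size in this study is unknown. The 1% to 5% missing-causality rates and the unclassified-reaction counts are assumptions. The 9.9% unrated share and the 84% to 94% range come from another study and depend on its two counts sharing a unit. In a descriptive study with no hypothesis on these outcomes, this is a moderate reporting defect. It is worth correcting because safety is the study's main purpose and the remedy needs no new data.

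**What to change.** Keep the no-imputation rule in 14.3 as the general case, and add these exceptions:

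1. An AE whose causality is still missing after query is counted as related in the related-AE summary, with the number so counted shown.
2. AEs with a missing reaction classification are listed separately. The primary incidence is given without them and, as a sensitivity bound, with them. No fixed time window is used to reclassify them.
3. Bleed and procedure ratings are tabulated over all treated bleeds or all procedures in the respective analysis set, with not rated as its own category. A bound counts unrated as None.

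The tabulation in item 3 already fits 14.3 and could go in the analysis plan; the bound, item 1 and the with-them figure in item 2 need the protocol change. The cost is a few sentences, one more table column and slightly less favourable figures. Item 1 may overstate related AEs, which is why the number so counted must be shown.

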14.4 Methods of Analysis for Primary and Secondary Outcome Measures

Statistical analysis will be descriptive in nature. Continuous variables will be described with means, standard deviations, minimum, first quartile, medians, interquartile ranges, third quartile, and maximum. Categorical variables will be expressed as frequencies and percentages. 95% confidence intervals of selected point estimates will be calculated. Paired statistical tests (parametric via t-test and/or non-parametric via Wilcoxon Signed-Rank test) will be employed to test for differences in infusion volume, time (to be captured in minutes and seconds) needed to mix and infuse FVIII, and satisfaction with ADVATE reconstituted in 5mL SWFI prior to enrolling in the study and ADVATE reconstituted in 2mL SWFI. Figures will be prepared to illustrate the patterns of data over time where appropriate.

14.4.1 Primary Outcome Measure

The primary outcome measure is to assess the incidence of all local and general, hypersensitivity and infusion-related reactions, irrespective of product-related causality for the AEs. The SAS will be employed to compute this outcome measure.

14.4.2 Secondary Outcome Measures

Each secondary outcome measure will be calculated by employing the applicable analysis set:

- Number of AEs considered by the investigator to be causally related (possibly or probably related) to ADVATE reconstituted in 2 mL SWFI, SAS
- Number of inhibitors in all subjects, SAS

- Number of inhibitors in PTPs (>50 EDs) with baseline FVIII < 1% and with no history of inhibitors prior to study entry, IAS1
- Number of inhibitors in PTPs (> 50 EDs) with baseline FVIII ≤ 2% and with no history of inhibitors prior to study entry, IAS2
- Subjective hemostatic effectiveness rating of excellent, good, fair, or none for each unique bleeding episode treated, EASBE
- Number of bleeding episodes treated with 1, 2, 3, ≥ 4 infusions of ADVATE reconstituted in 2 mL SWFI, EASBE
- Total units of ADVATE reconstituted in 2 mL SWFI administered to treat each bleeding episode, EASBE
- Overall effectiveness of prophylaxis in subjects who are on a prophylactic regimen for the full duration of the study, EASPT
- Global assessment rating of hemostatic effectiveness of ADVATE reconstituted in 2 mL SWFI (excellent, good, fair, or none) in surgical or dental procedures, EASSDP
- Change in FVIII treatment satisfaction and preference ratings from caregiver between ADVATE reconstituted in 5 mL and 2 mL SWFI, SAS
- Change in FVIII infusion volume and time to mix and infuse FVIII treatment between ADVATE reconstituted in 5 mL and 2 mL SWFI, SAS

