9. SUBJECT SELECTION, WITHDRAWAL, AND DISCONTINUATION

9.1 Inclusion Criteria

Subjects who meet ALL of the following criteria are eligible for this study:

- Subject has severe or moderately severe hemophilia A (baseline FVIII ≤ 2%)
- Subject is ≤ 12 years of age
- Subject's legally authorized representative(s) has provided written informed consent
- Subject is prescribed ADVATE and will only receive ADVATE reconstituted in 2 mL SWFI
- Documented history of prior exposure to ADVATE (for subjects ≤ 2 years old, at least 3 EDs to ADVATE; for subjects with ≤ 50 EDs, all prior EDs must be to ADVATE; for subjects with >50 EDs, the last 20 prior EDs must be to ADVATE)
- Documented evidence of negative inhibitor test result during ≤10 EDs prior to study entry

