10.3.1 Screening Visit

The following data will be collected at the **screening visit**:

- Date of birth
- Gender
- Race

- Ethnicity
- Height (cm)
- Weight (kg)
- Medical history
 - ➤ History of local and general infusion-related reactions
 - ➤ History of hypersensitivity reactions
 - ➤ History of FVIII inhibitor, if any
 - Date of inhibitor detection
 - o Date of inhibitor disappearance
 - o Titer at time of inhibitor detection
 - o Maximum historical titer
 - o Total FVIII ED at time of inhibitor detection
 - o FVIII product used at time of inhibitor detection
 - o FVIII regimen used at time of inhibitor detection
 - History of ITI therapy, if any, including FVIII product and regimen used
 - Most recent FVIII inhibitor titer
- Concomitant medications, including vaccinations
- Vaccination status for hepatitis A virus (HAV) and hepatitis B virus (HBV), if available
- Serology for hepatitis C virus (HCV) and human immunodeficiency virus type 1 & 2 (HIV-1/2), if available
- Baseline FVIII level
- FVIII mutation genotype, if available
- Family history of inhibitors
- Local laboratory cut off value for positive inhibitor titer
- Current treatment regimen (eg, prophylaxis or on-demand) with ADVATE reconstituted in 2 mL SWFI
 - Weight adjusted dose and dosing interval (frequency of infusions)
 - > Regimen start date
 - > Total FVIII ED at study entry
 - o For subjects with ≤50 EDs at study entry, exact number of total EDs must be recorded

- For subjects with >50 EDs, exact number of total ED is preferred, however, if this data is not available, one of the following ranges should be selected: 51 100, 101 150, > 150 ED
- > FVIII inhibitor titer at study entry
- > FVIII incremental recovery (IR; IU/dL per IU/kg) at study entry, if available
- Prior to study entry (maximal retrospective time period of 2 years)
 - > Treatment regimen (eg, prophylaxis, on-demand, or ITI)
 - Weight adjusted dose and dosing interval (frequency of infusions)
 - o Regimen start and end date
 - Name and/or type of products prior to ADVATE, if applicable
 - o Plasma-derived FVIII with VWF, intermediate purity
 - o Plasma-derived FVIII without VWF, high purity
 - o Recombinant FVIII: generation category; full-length vs. B-domain deleted molecule

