11.4 Clinical Laboratory Parameters

11.4.1 FVIII Inhibitor Titer

Documentation of a negative inhibitor test during ≤10 EDs before initiation of ADVATE reconstituted in 2 mL SWFI is an inclusion criterion. Thereafter, the investigators shall determine the frequency for inhibitor testing based on routine screening schedule, as appropriate within respective countries and subject to relevant clinical guidelines, or clinical signs. It is recommended that inhibitor testing is performed in the presence of clinical signs suggesting inhibitor development: increased bleeding tendency, high consumption, lack of response or efficacy, decreased IR, shortened half life. If an inhibitor is suspected, it is also recommended to look at FVIII IR. If the IR appears greatly reduced and/or no FVIII is detected, an inhibitor is suspected. It should be kept in mind that the normal PK range may be age-related, with children exhibiting different kinetics (shorter half-life and lower IR) compared to adults.

The inhibitor assay methods and reference standard used will be reported in the CRF. In the case a positive inhibitor titer is detected, a confirmatory test on a second, separately drawn sample should be performed. This second sample should be taken prior to any change of treatment and shortly (within 1 month) after the previous positive test. Results of FVIII IR and half-life tests should be recorded with associated washout period, FVIII dose administered and sampling times. All laboratory testing will be done at the local lab.

Negative inhibitor titer: any titer below the limit of inhibitor detection of the local lab; if local lab reference value is not available, any titer <0.6 BU by the Nijmegen modification Bethesda assay, or < 1 BU by a non-Nijmegen modification Bethesda assay.

Low-titer inhibitor titer: any titer higher than the limit of inhibitor detection of the local lab and ≤ 5 BU; if local lab reference value is not available, any titer ≥ 0.6 BU by the Nijmegen modification Bethesda assay, or ≥ 1 BU by a non-Nijmegen modification Bethesda assay.

High-titer inhibitor titer: any titer > 5 BU at any time after diagnosis.

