14.2.1 Safety Analysis Set

The safety analysis set (SAS) will consist of data for all subjects that receive at least 1 dose of ADVATE reconstituted in 2 mL SWFI.

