APPENDIX B: ADVATE 2 ML STUDY CAREGIVER SURVEYS

ADVATE 2 mL [reconstituted in 2 mL sterile water for injection (SWFI)]
Antihemophilic Factor (Recombinant) Plasma/Albumin Free Method (rAHF-PFM)

Octocog alfa (recombinant human coagulation factor VIII)

TITLE: ADVATE 2 mL (reconstituted in 2 mL SWFI)

POST-AUTHORIZATION SAFETY SURVEILLANCE STUDY

SHORT TITLE: ADVATE 2 mL PASS

PROTOCOL IDENTIFIER: 061101

NON-INTERVENTIONAL OBSERVATIONAL STUDY

Baxter BioScience	PROTOCOL NO 061101	SUBJECT IDENTIFICATION NO. SITE NO. SUBJECT NO.	Study Visit and Date: □ Follow-up Visit date:
----------------------	--------------------	---	---

ADVATE 2mL Study
Caregiver Survey
Baseline Assessment

Baxter BioScience	PROTOCOL NO 061101	SUBJECT IDENTIFICATION NO. SITE NO. SUBJECT NO.	Study Visit and Date: ☐ Follow-up
			Visit date:

We are interested in your experiences prior to enrolling in this study. Please complete the questions below with your prior ADVATE 5mL treatment in mind. Please answer each question to the best of your ability. There are no right or wrong answers.

Infusion Questions

1. Please select the number for each vial size you normally use to infuse your child's prescribed ADVATE dose. For example, if you are infusing 2 vials of 500 IU and 1 vial of 250 IU for your child, please complete the table as follows:

Number of Vials	EXAMPLE: Vial Sizes Needed to Infuse ADVATE Dose							
	250	250 500 1000 1500 2000 3000						
1								
2		\square						
3								
4								

Number of Vials	Vial Sizes Needed to Infuse ADVATE Dose					
	250	500	1000	1500	2000	3000
1						
2						
3						
4						

1	Baxter BioScience	PROTOCOL NO 061101	SUBJECT IDENTIFICATION NO. SITE NO. SUBJECT NO.	Study Visit and Date: ☐ Follow-up Visit date:
2.	Does your child h	nave a Central V	Venous Access Catheter / Port?	
3.	He infus I (parent	es himself /caregiver) info	ADVATE infusions? use him ssional infuses him	
4.	How long, on ave		ke to: child's prescribed ADVATE d seconds	ose?
	b) Infuse yo		scribed ADVATE dose after the seconds	needle is in place?
	c) Complet	e the whole inf minutes	fusion process (from setting up seconds	the vial(s) to cleaning up)?
5.	On average, what	percent of the	time do you lose access to your	child's vein after starting the infusion?
6.	If you've lost acc complete the infu		ld's vein, what percent of the tin	me do you re-stick the needle to

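### The paired 5 mL versus 2 mL caregiver comparisons are assigned to the SAS, but nothing requires or records prior 5 mL use, so some pairs may lack a valid 5 mL baseline

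*Protocol*

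**What the plan says.** Section 14.4.2 lists two caregiver outcomes with their analysis set: "Change in FVIII treatment satisfaction and preference ratings from caregiver between ADVATE reconstituted in 5 mL and 2 mL SWFI, SAS" and "Change in FVIII infusion volume and time to mix and infuse FVIII treatment between ADVATE reconstituted in 5 mL and 2 mL SWFI, SAS". Section 14.2.1 defines that set as "all subjects that receive at least 1 dose of ADVATE reconstituted in 2 mL SWFI". Section 14.4 plans paired tests (t-test and/or Wilcoxon signed-rank) of volume, mixing and infusion time, and satisfaction, comparing 5 mL before enrolment with 2 mL.

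The relevant eligibility criteria in Section 9.1 are "Subject is prescribed ADVATE and will only receive ADVATE reconstituted in 2 mL SWFI" and "Documented history of prior exposure to ADVATE (for subjects ≤ 2 years old, at least 3 EDs to ADVATE", followed by ADVATE conditions for children with up to 50 and more than 50 exposure days (EDs). None of these names the 5 mL reconstitution, and Section 9.2 does not exclude earlier 2 mL use.

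At screening (Section 10.3.1) the site records "Current treatment regimen (eg, prophylaxis or on-demand) with ADVATE reconstituted in 2 mL SWFI", with a start date. The two-year treatment history covers regimens, doses, dates and any products used before ADVATE, but not the volume in which earlier ADVATE was reconstituted.

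The baseline survey in Appendix B instructs the caregiver: "Please complete the questions below with your prior ADVATE 5mL treatment in mind". It has no option for a child who never used 5 mL and does not ask when 5 mL was last used.

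**The concern.** A paired comparison of 5 mL with 2 mL needs a real 5 mL experience on the baseline side of every pair. The criteria let in a child whose qualifying ADVATE exposure was entirely to 2 mL, or who changed to 2 mL well before enrolment. The baseline form takes 5 mL use for granted, so such a caregiver can leave items blank, answer about 2 mL, or answer from distant memory.

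At stake are the caregiver outcomes that carry the planned hypothesis tests in an otherwise descriptive study. Time and satisfaction differences could be diluted, a volume difference could be partly manufactured, and the preference items would ask some caregivers for a comparison they cannot make. Because earlier reconstitution volume is not captured, an analysis plan written later could not reliably identify and remove the affected pairs.

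**Working it through.** **1. The plan's own figure.** No sample size or power is given for the paired comparison. The only figure is the accrual target: 60 evaluable at 17% dropout (Section 14.1) gives 60/(1 − 0.17) = 72.29, rounded up to 73. It reproduces; no stated number is wrong. The problem lies in who is in the comparison.

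**2. Can an eligible child have no 5 mL history?** All three exposure conditions in Section 9.1 can be met on 2 mL alone: at least 3 EDs to ADVATE at age 2 or less; all EDs to ADVATE with up to 50 EDs; the last 20 EDs to ADVATE with more than 50.

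**3. Is it realistic in time?** Section 6.1 dates the 2 mL approvals from 15 November to 19 December 2011. The Synopsis plans initiation in November 2012, and Section 8.2 expects 36 months of recruitment, so to about November 2015. A child enrolled before the second birthday was born after the last approval if enrolled after December 2013 (December 2011 + 24 months). If age 2 is counted in completed years, the date is December 2014 (+ 36 months). On either reading, nearly all of the final recruitment year qualifies. Section 6.3 wants at least 15 of the 60 evaluable subjects to be 2 years or less: 15/60 = 25%.

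**4. Effect on time and satisfaction.** Let δ be the true mean difference in children who did switch, and p the share of pairs with no true change because both answers concern 2 mL. The expected mean is (1 − p)δ + p × 0 = (1 − p)δ. The protocol gives no value for p, so the shares below are assumptions.

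**5. Cost of restricting.** Starting from 60 pairs, n = 60(1 − p). With the same standard deviation, the confidence interval widens by √(60/n). The last column is the standardised paired difference detectable with 80% power (two-sided 5%, paired t-test).

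| Assumed p | Valid pairs n | Mean difference if invalid pairs are kept | CI width ratio after restriction | Detectable difference |
|---|---|---|---|---|
| 0% | 60 | 1.00 δ | 1.00 | 0.37 |
| 10% | 54 | 0.90 δ | 1.05 | 0.39 |
| 25% | 45 | 0.75 δ | 1.15 | 0.43 |
| 50% | 30 | 0.50 δ | 1.41 | 0.53 |

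The 25% row corresponds to all of the minimum 15 youngest children having used only 2 mL. Survey non-response would lower every count.

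**6. Effect on volume.** The survey asks for number and size of vials, not millilitres. If baseline volume is derived as vials × 5 mL (an assumption; the protocol states no rule), a child who only ever used 2 mL, with v vials at both times, contributes 5v − 2v = 3v mL of reduction that never took place. Here the error creates a difference instead of diluting one.

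**The case against.** The strongest counter-argument is that the protocol intends a switch at study entry. Section 11.4.1 states: "Documentation of a negative inhibitor test during ≤10 EDs before initiation of ADVATE reconstituted in 2 mL SWFI is an inclusion criterion". Section 11.1 identifies the study product with the 2 mL reconstitution, and Section 11.1.8 provides for events between consent and first study product exposure. Sections 8.1, 13.1 and 14.4 describe 5 mL before the study and 2 mL during it. The regimen and start date recorded at screening could also describe 2 mL being started at entry. This stands as evidence of intent, but not as a requirement: Section 9.1 ties the same inhibitor test to study entry and nowhere demands 5 mL use.

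It can also be said that the survey is optional, missing data are not imputed and the tests are paired, so blank baselines simply drop out. That is correct. The comparison will not run on every SAS subject, and bias arises only where a caregiver without 5 mL experience answers anyway. The form invites this by offering no way to say that the questions do not apply.

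A reader might infer that a quarter of pairs will be invalid. The documents do not support that. The 25% is only the minimum size of the youngest group. Birth after approval does not show that a child never used 5 mL, and Section 10.4 shows that 5 mL could still be used during the study. A reader might also infer that every difference is pulled toward zero. That need not hold for volume, and the 1 − p factor applies to means, not directly to the signed-rank test or to answers from distant memory.

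**Conclusion.** The gap is real. The protocol assigns a paired 5 mL versus 2 mL comparison to a set that neither requires nor records 5 mL use. Some pairs may therefore lack a valid baseline; the text does not establish that any will.

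The size depends on an unknown share p. Mean time and satisfaction differences fall to 1 − p of their true value, assuming that affected caregivers answer and that their true change is zero. The volume result may contain a reduction that did not occur, if volume is derived as vials × 5 mL. For affected caregivers the preference items cannot be answered meaningfully.

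The consequence is limited: these are secondary outcomes from an optional survey, and the primary safety outcome is untouched. The change is worthwhile because it is cheap and because the missing information is difficult to recover once the surveys are completed.

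**What to change.** - Add one item to the baseline survey: *Has your child used ADVATE 5 mL? If yes, date of last use.* If the answer is no, skip the 5 mL items at baseline and the preference items at follow-up.
- In Section 14.4.2, replace the SAS for these two outcomes by SAS subjects with prior 5 mL use and both surveys completed. Report the number of valid pairs and summarise never-5 mL children separately.
- Say in advance how the date of last use will be handled, for example by a sensitivity analysis. The documents offer no basis for a particular cut-off.
- Reconcile Sections 9.1, 11.1.8 and 11.4.1 on whether 2 mL is first given at study entry.

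The cost is one survey item, one analysis-set sentence and fewer pairs. At 45 instead of 60, confidence intervals widen by about 15%. Requiring both surveys loses nothing for the paired tests, which need both anyway.
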